8.0 Statistical Considerations

Paired t-tests will be used to determine differences between Cetirizine and Placebo trials for select dependent variables (e.g. mass, percent fat). A 2 x 2 (condition by time) repeated measures ANOVA will be used to determine pre- vs. post-test differences across conditions with select dependent variables (e.g. plasma histamine). A 2 x 5 (condition by time) repeated measures ANOVA with a priori simple main effects and a Bonferroni correction for multiple pairwise comparisons will be used to determine differences between conditions for select dependent variables (e.g. ventilation, VO_2 , SpO_2) obtained at each km of the 5km time trials.

A power analysis was completed using previous literature (Prefaut et al., *Med Sci Sports Exerc*, 1997). Their data examined the change in arterial PO_2 levels pre- and post-antihistamine, which relates to our outcome variable of arterial oxyhemoglobin saturation. From their data, we were able to calculate an interventional treatment effect (Cohen's d) of 0.61. Using a one tailed test to match our directional hypothesis, a power analysis with that treatment effect indicates that approximately 9 subjects will provide adequate statistical power (i.e. $1 - \beta > 0.80$) to show significant differences at the $p < 0.05$ level (experiment-wise error rate). With the potential for drop-outs and non-qualifiers after the initial $VO_{2\max}$ screening, we anticipate testing a total of 15 subjects.

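### The sample size of about 9 for power above 0.80 cannot be reproduced from the inputs the protocol states

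*Combined protocol and SAP*

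**What the plan says.** Section 8.0 (Statistical Considerations) bases the sample size on an earlier study of arterial PO2 before and after an antihistamine, "which relates to our outcome variable of arterial oxyhemoglobin saturation". From those data the investigators were able "to calculate an interventional treatment effect" of 0.61, labelled Cohen's d. The calculation is directional: "Using a one tailed test to match our directional hypothesis". It concludes that "a power analysis with that treatment effect indicates that approximately 9 subjects will provide adequate statistical power", defined as power above 0.80 at the p < 0.05 "level (experiment-wise error rate").

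The number to be tested is 15, the margin being explained by "With the potential for drop-outs and non-qualifiers" after the VO2max screening. No loss rate is given.

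The same section assigns SpO2, the outcome the power analysis refers to, to this analysis: "A 2 x 5 (condition by time) repeated measures ANOVA with a priori simple main effects and a Bonferroni correction for multiple pairwise comparisons", on values "obtained at each km of the 5km time trials".

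Four things are not stated in Section 8.0 or elsewhere: which test was powered, which standard deviation 0.61 is divided by, any within-subject correlation, and how many repeated measurements the calculation assumed.

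**The concern.** Section 2.0 describes a repeated measures design in which each subject receives both Cetirizine and placebo, so the natural first check is a one-tailed paired t-test with an effect of 0.61. That test needs roughly twice the stated number of subjects, a gap too wide for rounding or for the word approximately to cover.

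What is at stake is how the result will be read. The protocol presents 9 completers as adequate and 15 as cover for losses. If the direct reading is the intended one, a trial that ends with 9 completers has about an even chance of detecting the assumed effect while being described as adequately powered, and a null result could be mistaken for evidence of no effect.

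**Working it through.** **Inputs from Section 8.0:** d = 0.61; one-tailed; alpha 0.05; power above 0.80; stated n about 9; 15 to be tested. **Assumptions made here, not in the protocol:** every correlation r below, equal SDs in the two conditions, f = d/2, and sphericity.

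**Reading A: 0.61 is the standardised paired difference (dz), one-tailed paired t-test.** Power = P(T > t(0.95, n−1)), where T is noncentral t with n−1 degrees of freedom and noncentrality 0.61 × √n.

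| Completers | Noncentrality | Critical t | Power |
|---|---|---|---|
| 9 | 0.61 × 3 = 1.830 | 1.860 | 51.1% |
| 12 | 2.113 | 1.796 | 63.2% |
| 15 | 2.363 | 1.761 | 72.6% |
| 18 | 2.588 | 1.740 | 79.9% |
| 19 | 2.659 | 1.734 | 81.9% |

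The plan's 9 is not reproduced; the first n above 80% is 19. The cruder normal approximation, ((1.645 + 0.842)/0.61)² = 16.6, gives 17. A two-tailed paired test needs 24, and two parallel arms would need 34 per arm one-sided. The paired effect detectable with 80% power is 0.91 at 9, 0.77 at 12 and 0.68 at 15.

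The alpha is described as experiment-wise. If five per-kilometre contrasts were each tested one-tailed at 0.05/5 = 0.01 (an assumption), power would be 21% at 9 and 42% at 15, and 80% would need 30.

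**Reading B: 0.61 is on the raw-SD scale, one-tailed paired t-test.** With equal SDs, dz = 0.61/√(2(1−r)).

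| r | dz | Power at 9 | Power at 15 | n for 80% |
|---|---|---|---|---|
| 0.5 | 0.610 | 51% | 73% | 19 |
| 0.6 | 0.682 | 59% | 81% | 15 |
| 0.7 | 0.788 | 70% | 89% | 12 |
| 0.75 | 0.863 | 76% | 94% | 10 |
| 0.8 | 0.964 | 84% | 97% | 9 |

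Solving for 80% at 9 gives dz = 0.909, so r = 1 − (0.61/0.909)²/2 = 0.775. For 15 completers, dz = 0.675 and r = 0.59.

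**Reading C: a repeated measures ANOVA was powered.** One group, m measurements, noncentral F with λ = f²·n·m/(1−r) and degrees of freedom m−1 and (n−1)(m−1), alpha 0.05. Example: f = 0.305, m = 5, r = 0.7, n = 9 gives λ = 0.093 × 9 × 5/0.3 = 13.95 and power 80.4%.

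| f | m | r | Power at 9 | Power at 15 | n for 80% |
|---|---|---|---|---|---|
| 0.305 | 2 | 0.5 | 36% | 59% | 24 |
| 0.305 | 2 | 0.7 | 55% | 81% | 15 |
| 0.305 | 2 | 0.8 | 72% | 93% | 11 |
| 0.305 | 5 | 0.5 | 56% | 83% | 15 |
| 0.305 | 5 | 0.6 | 67% | 91% | 12 |
| 0.305 | 5 | 0.7 | 80% | 97% | 9 |
| 0.305 | 10 | 0.5 | 78% | 97% | 10 |
| 0.305 | 10 | 0.6 | 88% | 99% | 8 |
| 0.61 | 2 | 0.3 | 77% | 96% | 10 |
| 0.61 | 2 | 0.4 | 83% | 98% | 9 |
| 0.61 | 2 | 0.5 | 89% | 99% | 8 |

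The f = 0.305, m = 2 rows are the Cetirizine versus placebo effect. In a 2 × 5 repeated measures ANOVA the condition F equals the squared paired t on each subject's mean over the five kilometres (both 11.434 in a simulated data set of 9), so these rows equal a two-sided paired t-test. On them, 9 needs r of about 0.84.

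The rows that return about 9 each need an unstated m and r. The rows with m = 5 or 10 test differences among all the means, not Cetirizine against placebo, and f = d/2 is strictly a two-level identity. The rows with f = 0.61 contradict the label Cohen's d.

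**The case against.** The best defence is that this is incomplete reporting, not a wrong calculation. Cohen's d is often a raw-SD measure, and a high within-subject correlation is plausible in a crossover. At r = 0.8, 9 completers give 84% power and 15 give 97%. The standardiser, and perhaps the correlation, may be in the cited study, which is not available here. The wording is also hedged, and 10 subjects (r = 0.75) could pass for approximately 9.

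Most of this stands, and it limits the conclusion: the documents do not show that 9 is wrong or that the trial is underpowered. It does not rescue the paragraph. On the raw-SD reading, power at 9 runs from 51% at r = 0.5 to 84% at r = 0.8, so the unstated correlation decides whether the claim is true.

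It is also fair to say that the two-level ANOVA figures of 24, 15 and 11 are two-sided and not like-for-like with the stated one-tailed test. The one-tailed counterparts are 19, 12 and 9 at r = 0.5, 0.7 and 0.8, which are the raw-SD results again. The F-test is non-directional, so an ANOVA calculation would still have to be squared with the one-tailed statement.

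A last defence is that 15 subjects make up any shortfall. That figure already includes expected losses. Even 15 completers give 73% on the direct reading, and on the raw-SD reading they reach 80% only from r of about 0.59.

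**Conclusion.** The concern holds: the stated sample size does not follow from the stated inputs. With 0.61 as the paired effect, power is 51% at 9 and stays below 80% for every number of completers from 9 to 15. The 73% at 15 is a ceiling, because some of the 15 are expected to be lost. With 0.61 on the raw-SD scale and equal SDs, 9 needs a correlation of about 0.775 or higher. Across the ANOVA settings tried, power at 9 runs from 36% to 89%.

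Confidence is high that 9 is not reproducible as written. Whether 9 is correct under some unstated assumption cannot be settled from the documents. This should be fixed, since no other sample-size justification is given.

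**What to change.** Trace how 0.61 and 9 were derived, then rewrite the power paragraph in Section 8.0. It should name the test and the effect that was powered, the standardiser of 0.61, the alpha used (single comparison or after correction), and any assumed correlation with its source. What follows depends on the answer:

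- **0.61 is the paired effect.** Replace the claim with wording such as: *With a standardised paired difference of 0.61 (one-tailed paired t-test, alpha 0.05), 9 completers give 51% power and 15 give 73%; 80% power needs 19. With 15 completers the effect detectable with 80% power is about 0.68.*
- **0.61 is on the raw-SD scale.** Show power at 9 and 15 over a range of correlations, as in the Reading B table. Keep 9 as adequate if the sourced correlation is about 0.775 or higher, or about 0.75 if 10 is accepted as approximately 9.
- **A repeated measures ANOVA was powered.** State which effect (condition, time or interaction), f, the number of measurements, the correlation and alpha. Explain how these fit the one-tailed statement, and give the resulting power at 9 and 15.

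The cost is one paragraph and a check of the original calculation. The rewording itself needs no extra subjects and no design change. The downside is that the stated power may be less favourable. If the first case applies, staying at 15 is a decision to accept at most 73% power, and the text should say so.

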2.0 Rationale and Specific Aims

Specific Aim #1 – Determine the effect of Cetirizine (Zyrtec®) on exercise performance and arterial oxygenation with acute exposure to a simulated altitude

For this project, healthy subjects will perform steady state and progressive work rate exercise, endurance performance time trials, and repeated sprint performance time trials in the laboratory at a simulated altitude of 3000m (9900ft) after dosing with 10 mg of Cetirizine or a placebo in a repeated measures design. Non-invasive techniques (pulse oximetry, near-infrared spectroscopy [NIRS]) will be utilized to measure changes in arterial oxyhemoglobin saturation and skeletal muscle oxygenation at the level of the microvasculature during exercise.

It is expected that after Cetirizine, blood and muscle microvascular oxygenation during heavy exercise will improve compared to placebo, ultimately improving exercise performance at altitude.

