on the cycle ergometer at a self-selected speed for 10 minutes. Following the warm-up, subjects will be fitted with a chest strap heart rate monitor, an oro-nasal face mask, a pulse oximeter sensor, and near-infrared spectroscopy optodes. Subjects will then be asked to complete two 5-minute cycling bouts at a constant, moderate intensity (as will be determined individually according to each subject's maximal oxygen uptake test performed on Session 1, details below). Subjects will be allowed 5 minutes of passive recovery after each of the 5-minute cycling bouts. Following the second recovery period, subjects will be asked to ride 5km, completing the distance in as short of a time as possible. Subjects will be allowed to shift gears on the bike at will and pedal at any RPM desired. Feedback on distance completed will be shown on a video monitor and verbally announced every 1km. During the TT, respiratory flow-volume measures will be completed by having the subjects complete two inspiratory capacity (IC) maneuvers near the end of each kilometer of the TT. Immediately following the TT, approximately 5 ml of blood will be drawn from an antecubital vein.

Demographic and screening variables: Age, height, weight, sex, body mass index, body composition (estimated percent lean body mass and fat mass), pulmonary function measures (total lung capacity, vital capacity, forced expiratory volume in one second, lung diffusing capacity, and maximal voluntary ventilation).

Dependent variables: exercise metabolic measures (VO₂, VCO₂, ventilation, heart rate), dyspnea and rating of perceived exertion during the 5km TT, time to completion of the 5km TT, power output during the 5km TT, muscle oxygenation, plasma histamine levels.

Specific Measures:

Height and weight: Height will be measured using a standard wall mounted, sliding height measuring board (stadiometer). Weight will be measured by an electronic scale.

Body composition: Subject stands in bare feet on an electrode imbedded scale (Tanita) and holds on to electrode imbedded handles. An unnoticeable electrical current is passed through the subject for 2 seconds, from which resistance to electrical flow is measured and body composition is estimated.

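### Does the experiment-wise 0.05 for SpO2 fail because the two constant-load bouts have no stated analysis or correction?

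*Combined protocol and SAP*

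**What the plan says.** Section 8.0 takes its effect size from arterial PO2 in a cited study, "which relates to our outcome variable of arterial oxyhemoglobin saturation". The power calculation is one-tailed, with significance at the p < 0.05 "level (experiment-wise error rate".

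SpO2 is named for one analysis only: the 2 x 5 (condition by time) repeated measures ANOVA of variables "obtained at each km of the 5km time trials". That analysis uses simple main effects chosen in advance and "a Bonferroni correction for multiple pairwise comparisons". The other two procedures carry no correction. One is the 2 x 2 pre/post ANOVA, with plasma histamine as its example. The other reads "Paired t-tests will be used to determine differences between Cetirizine and Placebo trials for select dependent variables (e.g. mass, percent fat").

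Section 5.0 places two five-minute constant-load bouts in hypoxia before the time trial in Sessions 2 and 3, at 60% and 75% of VO2max. Before these bouts subjects are "fitted with a chest strap heart rate monitor, an oro-nasal face mask, a pulse oximeter sensor, and near-infrared spectroscopy optodes". Under Aim 1 in Section 2.0, "healthy subjects will perform steady state and progressive work rate exercise", among other tasks, and the non-invasive techniques "will be utilized to measure changes in arterial oxyhemoglobin saturation and skeletal muscle oxygenation at the level of the microvasculature during exercise". Section 8.0 does not mention the bouts, and no outcome is called primary or secondary.

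**The concern.** An error rate described as experiment-wise should cover every test on which a claim could rest. Here SpO2 can be compared in three settings per treatment session, and the correction reaches only one of them. The 2 x 2 ANOVA is pre/post and the 2 x 5 is per km, so the sentence that would fit a per-workload comparison is the uncorrected paired t-test. The variable lists in Section 8.0 are open-ended examples, so nothing rules such a test out.

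At stake is the reading of a split result. If one bout favoured cetirizine and the time trial did not, the bout could be reported as improved oxygenation at a nominal 0.05, with no rule fixed beforehand to prevent it.

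**Working it through.** **The plan's own figure.** Section 8.0 gives about 9 subjects for more than 80% power at d = 0.61, one-tailed 0.05. Read as a standardised paired difference, 0.61 gives 51% power at n = 9, and 19 subjects are needed. If 0.61 is on the raw-SD scale with a within-subject correlation of 0.8 (assumed), then dz = 0.61/sqrt(2 x 0.2) = 0.964 and n = 9 is reached. That is a separate matter; the error-rate question does not depend on it.

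**Step 1: what the plan announces for SpO2.** There are five per-km comparisons between conditions. Bonferroni gives 0.05/5 = 0.01 each.
- Upper bound: 5 x 0.01 = 5%.
- If independent: 1 - 0.99^5 = 4.9%.

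The per-km family therefore holds 0.05.

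**Step 2: add two bout tests that the plan does not announce.** Assume a paired t-test at 0.05 for each bout, all nulls true, and any positive result counted as a claim. The documents state none of these rules and give no correlations.
- Five km tests at 0.01 plus two bout tests at 0.05, independent: 1 - 0.99^5 x 0.95^2 = 1 - 0.9510 x 0.9025 = 14.2%.
- Time trial taken as one test of the condition main effect at 0.05, plus two bouts, independent: 1 - 0.95^3 = 14.3%.

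With equally correlated paired differences (simulation; ranges cover n = 9 and n = 15, one- and two-sided):

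| Correlation | Five km tests at 0.01 + two bouts | One time-trial test + two bouts |
|---|---|---|
| 0.5 | 11.1 to 12.3% | 12.0 to 13.0% |
| 0.8 | 8.3 to 9.2% | 9.5 to 10.4% |
| 1 | 5% | 5% |

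Independence is implausible for measurements on the same subjects in the same sessions, so 14% is an upper end. The version that follows the plan's per-km procedure gives the lower figures once the tests are correlated.

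**Step 3: does the text make the bout tests part of the claim?**
- Section 2.0 states the expected improvement for heavy exercise. Section 5.0 describes the bouts as moderate.
- Section 8.0 names SpO2 only for the time trial. The examples for the paired t-test are mass and percent fat.
- The Aim 1 sentence that mentions steady-state work is a poor guide to planned comparisons. It also lists progressive exercise and repeated sprints at simulated altitude after dosing. Section 5.0 puts the progressive test in Session 1, in normoxia and before any dosing, and describes no sprints.

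**Step 4: what formal correction would cost.** Suppose the bouts were made formal tests in a four-test Holm family (SpO2 and one muscle-oxygenation variable at two workloads). The first step is 0.05/4 = 0.0125. With a standardised paired difference of 0.61 (assumed at a bout), one-sided power falls from 72.6% to 46.4% at n = 15, and from 51.1% to 24.5% at n = 9. Treating the bouts as supportive spends no alpha and needs no adjustment.

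**The case for a change.** The strongest reply is that the plan itself uses the term experiment-wise, so it should say which family is covered. The bouts are a real part of Aim 1, the oximeter is on before they start, and muscle oxygenation during constant-load work is explicit in Section 5.0. The data will very likely exist and someone will look at them. The moderate label is also arguable, because workloads set from a maximum measured in normoxia are ridden in hypoxia. A few sentences would settle the matter.

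Much of this stands as description. No primary outcome is named, the scope of experiment-wise is undefined, and the bouts have no stated analysis. The term is equally unsupported for ventilation, VO2, time-trial time and histamine. Nor does the plan reconcile a one-tailed sizing with an ANOVA F test, which has no direction.

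What does not stand is the step from silence to lost error control. That step needs tests the plan does not list and a rule that any one of them suffices. A fuller remedy would also bring its own problem. Making the condition main effect the confirmatory test, with four new bout tests beside it, would leave the planned per-km simple main effects without a stated role. That is a debatable change of analysis, and no fault in the present one requires it.

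**Conclusion.** The concern does not call for a change. Followed as written, Section 8.0 gives a randomised within-subject SpO2 comparison in the time trial, which is the setting that best matches the heavy-exercise hypothesis, and the per-km family is held at 5%. Inflation to roughly 8 to 14% is conditional on two assumptions absent from the documents: that uncorrected SpO2 tests are run at both bouts, and that a positive result in any setting counts as the claim. What remains is missing detail. The ordinary reading is that time-trial SpO2 carries the claim, constant-load SpO2 and muscle oxygenation are supportive or descriptive, and experiment-wise refers to the Bonferroni-corrected per-km comparisons. This conclusion would change if a report rested its oxygenation claim on a bout result alone.

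### Section 8.0 calls p < 0.05 an experiment-wise error rate, but nothing controls error across outcomes and no outcome is named primary, so 0.05 is at best a per-outcome rate

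*Combined protocol and SAP*

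**What the plan says.** The power paragraph of Section 8.0 says the planned number of subjects is enough to detect differences at a p < 0.05 "level (experiment-wise error rate"). This is the only place where an error rate is named. The same paragraph specifies the test direction ("Using a one tailed test to match our directional hypothesis") and the effect size ("interventional treatment effect (Cohen's d) of 0.61"). It links the cited data to this study through a measure "which relates to our outcome variable of arterial oxyhemoglobin saturation".

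The analysis paragraph of Section 8.0 assigns paired t-tests, 2 x 2 ANOVAs and 2 x 5 ANOVAs to selected variables, named only by example. One adjustment appears, attached to the 2 x 5 ANOVA on per-kilometre data: "with a priori simple main effects and a Bonferroni correction for multiple pairwise comparisons". No alpha is given for an individual variable.

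Section 5.0 gives the outcome list, beginning "Dependent variables: exercise metabolic measures". It has ten entries and SpO2 is not among them. Section 2.0 states one aim with two domains, exercise performance and arterial oxygenation, and ranks neither. The word primary is not applied to any outcome.

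**The concern.** An experiment-wise rate describes the study as a whole: the chance that any of its tests gives a false positive. The Bonferroni step in Section 8.0 works across comparisons within one variable. It does nothing when SpO2, muscle oxygenation, time-trial time and time-trial power are each examined in turn. The plan has no ordering of outcomes, no gatekeeping and no division of alpha, and the tested variables are identified only by example. The label therefore states a property that the described analysis does not have.

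What is at stake is the wording of the eventual claim. A significant result on one of several outcomes could be reported as protected at an experiment-wise 5% when that protection was never built in. With no primary outcome named, the reader of the report also cannot tell which result the study was meant to stand on.

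**Working it through.** **Inputs.**
- Alpha: 0.05, labelled experiment-wise (Section 8.0).
- Sidedness: one-tailed in the power analysis; not stated for the analyses (Section 8.0).
- Ten listed variables (Section 5.0): VO2, VCO2, ventilation, heart rate, dyspnea, RPE, time-trial time, time-trial power, muscle oxygenation, plasma histamine. SpO2 (Section 8.0) makes 11.
- Variables bearing directly on Aim 1 (Section 2.0): SpO2, muscle oxygenation, time-trial time, time-trial power, so 4.
- Subjects: about 9 for the power target, 15 planned (Section 8.0).
- Assumed, not in the documents: one drug test per variable at 0.05, and a common between-variable correlation from 0 to 0.9.

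**The plan's figure.** An experiment-wise rate of 0.05 follows only if a single test is made or if the tests are adjusted jointly. Section 8.0 provides for neither.

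**Independent outcomes.** The chance of at least one false positive among k tests is 1 - 0.95^k:
- k = 2 (SpO2, time-trial time): 1 - 0.95^2 = 9.8%
- k = 4 (Aim 1 variables): 1 - 0.95^4 = 18.5%
- k = 11: 1 - 0.95^11 = 43.1%

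**Correlated outcomes.** Null trials of k equicorrelated paired t-tests were simulated at n = 9 and n = 15. For k = 11:

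| Correlation | Two-sided | One-sided |
|---|---|---|
| 0.3 | 38-39% | 33-34% |
| 0.5 | 32-33% | about 27% |
| 0.7 | about 24% | 20-21% |
| 0.9 | 14-15% | 12-13% |

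At correlation 0.9 the smaller families give about 7% (k = 2) and about 9-10% (k = 4), across one- and two-sided tests. The ranges from correlation 0.9 to 0 are therefore about 7-10%, 9-19% and 12-43%.

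**Price of making the label true for all 11.** Bonferroni would need 0.05/11 = 0.00455 per variable. Taking d = 0.61 as the standardised paired difference, which the plan does not confirm, one-sided power at that level is about 13% at n = 9 and 30% at n = 15; 80% power needs n = 36.

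**Power of a single SpO2 test.** On the same reading of d, a one-sided paired t-test at 0.05 has power of 51% at n = 9 and 73% at n = 15. That the 51% differs from the plan's own power target is a separate matter. It is used here only to cost the options under the fix.

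**The case against.** The phrase occurs once, in a sentence that sizes the study on one outcome with one one-tailed test. It may refer loosely to the Bonferroni-protected comparisons within an ANOVA, described in the paragraph before. That stands as a caution: the plan does not expressly promise 5% over 11 variables. But on that reading the label is still wrong for the study as a whole and needs correcting.

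A reader might infer that any of the 11 variables crossing 0.05 would count as support for Aim 1, with a 24-43% chance of that happening falsely. The documents do not support this. Section 2.0 expects better blood and muscle oxygenation and, as the end result, better performance. A chance difference in heart rate, VCO2 or plasma histamine would not meet that expectation. The number of variables to be tested is open, and testing each at 0.05 is an inference. A floor of 24% also needs two-sided tests and a correlation no higher than about 0.7, whereas the only stated test direction is one-tailed, and closely linked measures such as time-trial time and power could correlate more strongly.

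If two-sided tests are used and only favourable results are counted, the independent-case figures fall to 1 - 0.975^4 = 9.6% for four variables and 1 - 0.975^2 = 4.9% for two. The fair comparison is then 2.5% for a single test, so the inflation remains although the absolute size is small.

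It can also be said that SpO2 is already primary in effect, since the study is sized on it. Section 8.0 comes close to saying so, but Section 5.0 leaves SpO2 off the list and Section 2.0 gives performance equal standing.

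**Conclusion.** The concern holds in a limited form. Section 8.0 names an experiment-wise rate, describes no control across outcomes and designates no primary outcome; 0.05 is therefore at best a per-outcome rate.

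The size depends on which outcomes form the family. For those that Aim 1 turns on, it is about 9-19%, or about 7-10% if only SpO2 and time-trial time are counted. The 12-43% range applies to all 11 variables, and its upper end requires independence, which is implausible for measures taken in the same ride. All three ranges assume testing at 0.05 per outcome and a common correlation between 0 and 0.9, with the sidedness left open.

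The conclusion about the label rests on the text and needs none of these assumptions. This should be corrected before analysis; it affects what may be claimed, not the conduct of the study.

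**What to change.** In Section 8.0:
- Delete the experiment-wise label and state that 0.05 applies per outcome, with no control across outcomes.
- Name SpO2, the variable the study is sized on, as the single primary outcome. State the one condition contrast to be tested at 0.05 and its sidedness.
- Report all other variables as secondary, with no experiment-wise claim.

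In Section 5.0, add SpO2 to the dependent variables.

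This takes a few sentences and no new data or subjects. It leaves the primary SpO2 test at the full 0.05. The downside is that results other than SpO2, including time-trial time, carry no confirmatory claim.

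If the sponsor wants a confirmatory claim on time-trial time, which Section 2.0 treats as the ultimate result, there are two routes, and the choice is the sponsor's. Testing it only after a significant SpO2 result keeps SpO2 at 0.05. However, with SpO2 power of 51% (n = 9) or 73% (n = 15), the gate would stay closed about 49% or 27% of the time even if the SpO2 effect is real. Making the two co-primary at 0.025 each avoids the gate but lowers one-sided SpO2 power to about 36% or 59% on the same reading of d. Bonferroni across all 11 variables is not advised, given the power shown above.
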